6.10.3. Hypoglycemic Events and Other Adverse Events

The analysis plans for the following AEs are discussed in Section 6.10.3.1:

- hypoglycemia
- injection site reaction

These AE analyses will be similar to the TEAE analyses, refer to [Table ITSZ.6.3](#) for the requirement of analysis data for a specific analysis period.

6.10.3.1. Hypoglycemia

Hypoglycemia will be described using the following definitions:

- **Level 1:** Glucose <70 mg/dL (3.9 mmol/L) and ≥54 mg/dL (3.0 mmol/L)
- **Level 2:** Glucose <54 mg/dL (3.0 mmol/L)
- **Level 3: Severe hypoglycemia:**

Participants have altered mental status and cannot assist in their own care, may be semiconscious or unconscious, or experience coma with or without seizures, and require assistance of another person to actively administer carbohydrate, glucagon, or other resuscitative actions. Glucose measurements may not be available during such an event, but neurological recovery attributable to the restoration of blood glucose concentration to normal is considered sufficient evidence that the event was induced by a low blood glucose concentration.

- The determination of a hypoglycemic event as an episode of severe hypoglycemia, as defined above, is made by the investigator based on the medical need of the participant to have required assistance and is not predicated on the report of a participant simply having received assistance.
- All episodes of severe hypoglycemia must be reported as SAEs on the AE eCRF page and on the SAE eCRF page.

Any events of severe hypoglycemia categorized as level 3 per the evaluation of investigators will be collected from ICF signing to Visit 801.

Level 1 and level 2 hypoglycemia will be analyzed based on glucose data from the CGM sensor session. Derivation and analysis of Level 1 and Level 2 hypoglycemia (derived for duration (in minutes) and percentage of time in Level 1 or Level 2) and other CGM endpoints are described in Section 6.13.

Severe hypoglycemia will be collected as AEs in eCRF and all episodes of severe hypoglycemia will be considered as SAEs. Table ITSZ.6.4 provides detailed statistical methods for severe hypoglycemia. Summary statistics will be provided for severe hypoglycemia events from first dose to last dose of IP.

A listing of patients with at least 1 severe hypoglycemia reported (as SAE) from Visit 3 through Visit 801 will be provided.

A list of MedDRA PTs will be used for the narrow search of potential severe hypoglycemia in spontaneously reported AEs. The events identified through the search strategy that are also reported as SAEs will be summarized.

Table ITSZ.6.4. Summary of Analyses for Severe Hypoglycemia

Endpoint	Analysis Period	Statistical Method
Rate of severe hypoglycemic events (per patient per year / 100 years)	Treatment Period	Summary statistics for exposure adjusted rate per year / 100 years (calculated for each patient by total number of events divided by total exposure) will be provided
Incidence of severe hypoglycemic events	Treatment Period	Summary statistics for proportion of patients with severe hypoglycemia will be reported.

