Participants who discontinue investigational product (IP) permanently before completion of the treatment period for any reason will also be discontinued from the study. An (ET) visit should be conducted as soon as reasonably possible. After the ET visit, a safety follow-up assessment (Visit 801) should be conducted approximately 1 week after the ET Visit.

Transcribing Data into the eCRF at the ET Visit

At the early termination visit, the investigator should transcribe the following data from the day before visit into the eCRF:

- ICR
- ISF
- DIA
- LY900014 dose

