7.2. Participant Discontinuation/Withdrawal from the Study

A participant will be withdrawn from the study in the following circumstances:

- if he or she uses a non-study rapid-acting insulin for a period greater than 48 hours during the treatment period.
- if he or she loses contact with the site for more than 10 days.
- if he or she uses prohibited concomitant medication during the study as specified in Section 6.5.

A participant may withdraw from the study:

- at any time at his or her own request
- at the request of his or her designee (for example, parents, or legal guardian)
- at the discretion of the investigator for safety, behavioral, compliance, or administrative reasons
- if the participant becomes pregnant during the study
- if enrollment in any other clinical study involving an investigational product or enrollment in any other type of medical research judged not to be scientifically or medically compatible with this study
- if the participant, for any reason, requires treatment with another therapeutic agent that has been demonstrated to be effective for treatment of the study indication, discontinuation from the study occurs before introduction of the new agent
- if the investigator, after consultation with the sponsor-designated medical monitor, determines that a systemic hypersensitivity reaction has occurred related to study drug administration, the participant should be permanently discontinued from the investigational drug.

If the participant withdraws consent for disclosure of future information, the sponsor may retain and continue to use any data collected before such a withdrawal of consent. If a participant withdraws from the study, he or she may request destruction of any samples taken and not tested, and the investigator must document this in the site study records.

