5.2. Determination of Sample Size

Approximately 34 participants will be assigned to study treatment such that 30 evaluable participants will complete the maintenance period, assuming a 10% dropout rate.

The study is not strictly powered to demonstrate a statistically significant change from baseline in the primary endpoint (percentage of time with glucose within 70 to 180 mg/dL) because of the exploratory nature of the study.

Using a standard deviation of 12%, the sample will provide approximately 80% coverage probability that the half-width of the 95% confidence interval (CI) of the change from baseline in the primary endpoint falls within 4.93%.

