- for data collected as running records with an exact date such as adverse events (AEs) where the date of the measures is not tied with the date of an office visit, postbaseline

data with date \leq (last study drug dose date) will be considered as data on IP for the treatment period.

An analysis of covariance (ANCOVA) will be used to analyze continuous variables that are planned to be collected only for baseline and endpoint. The model will include baseline as a covariate.

A restricted maximum likelihood based, mixed model repeated measures (MMRM) analysis will be used to analyze continuous longitudinal variables collected only at baseline and more than one scheduled post-baseline visits according to SoA in Section 1.3. All the longitudinal observations at each scheduled post-baseline visit will be included in the analysis. The model for the analysis of the primary efficacy endpoint will include the fixed class effect of visit, and the random effect of patient. An unstructured covariance structure will be used to model the within patient errors. Significance tests will be based on least squares (LS) means and Type III tests. SAS PROC MIXED will be used to perform the analysis. If this analysis fails to converge, the following covariance structures will be tested in order:

- Toeplitz with heterogeneity
- Autoregressive with heterogeneity
- Compound symmetry with heterogeneous variances
- Toeplitz
- Autoregressive
- Compound symmetry without heterogeneous variances

The first covariance structure that converges will be used. The Kenward Roger approximation will be used to estimate denominator degrees of freedom. If the analysis still does not converge with Compound symmetry without heterogeneous variances, only summary statistics will be provided.

For continuous measures, summary statistics will include sample size, mean, standard deviation, median, minimum, and maximum for both the actual and the change from baseline measurements. Least square (LS) means and standard errors derived from the analysis models will also be displayed for the actual and the change from baseline measurements.

For categorical measures, summary statistics will include sample size, frequency, and percentages. No statistical analyses will be conducted for baseline and endpoint comparison.

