6.10. Safety Analyses

6.10.1. Extent of Exposure

Duration of exposure to study drug will be summarized based upon eCRF data. The following summary statistics will be provided: n, mean, SD, median, minimum, maximum, and sum (that is, total patient-years of exposure). The number and proportion of patients falling into the following different exposure categories will also be summarized: <14 days (>0 and <14 days), ≥14 and <35 days, ≥35 and <46 days, and ≥46 days.

Patients who complete the study treatment period are required to complete a safety follow-up visit without study drug; and patients who discontinue the IP unplanned are required to discontinue from the study (ITSZ Protocol 7.1).

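### SAP Table ITSZ.6.4 gives the severe hypoglycemia rate only as a summary of per-patient ratios, with no total-events over total-patient-years rate and no confidence interval

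*SAP*

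**What the plan says.** The first row of SAP Table ITSZ.6.4 (Section 6.10.3.1) is labelled "Rate of severe hypoglycemic events (per patient per year / 100 years"). Its method is summary statistics of a rate "calculated for each patient by total number of events divided by total exposure". SAP 6.1 says what such statistics are: "For continuous measures, summary statistics will include sample size, mean, standard deviation, median, minimum, and maximum". The window is set in the text above the table: "Summary statistics will be provided for severe hypoglycemia events from first dose to last dose of IP". The second row of the table is the proportion of participants with an event.

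Total exposure is planned separately. The exposure summary in SAP 6.10.1 includes "minimum, maximum, and sum (that is, total patient-years of exposure"), but nothing links that total to the severe hypoglycemia count. SAP 6.1 sets a general two-sided 95% level for intervals without naming a method for an event rate, and SAP 6.10.2 describes the adverse event analyses as descriptive.

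The documents allow for unequal exposure. SAP 5.2 sizes the study "assuming a 10% dropout rate", and the exposure categories in SAP 6.10.1 begin below 14 days. Protocol 4.1.1 states: "Participants who discontinue investigational product (IP) permanently before completion of the treatment period for any reason will also be discontinued from the study".

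**The concern.** A mean of individual ratios counts a participant treated for 7 days as heavily as one treated for 46. It equals events per patient-year of observation only when all exposures are equal. The row label, in patient-years and per 100 years, invites the reader to take the figure as the pooled rate.

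The row matters because severe hypoglycemia is the only hypoglycemia level with a planned event rate; Levels 1 and 2 are analysed as duration and percentage of time on CGM. The mean would be biased upward if severe events led to early stopping. Protocol 7.2 leaves room for that, since withdrawal is possible "at the discretion of the investigator for safety, behavioral, compliance, or administrative reasons", but does not require it.

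The missing interval is a separate gap. If no severe event occurs, the planned row shows a mean of 0 and an SD of 0, and nothing in it tells the reader how little exposure stands behind that zero.

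**Working it through.** **Inputs.** From SAP 5.2: 34 assigned, 30 evaluable, 10% dropout. The 34 reproduces: 30 / (1 − 0.10) = 33.3, rounded up. From SAP 5.1: 35 days of titration plus 11 of maintenance, so 46 days of treatment. The documents state no expected severe hypoglycemia rate or event count, so there is no planned figure to reproduce for this row. Stop days and event counts below are assumptions, shown as a range. A year is 365.25 days.

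**Formulas.** For participant i with y_i events and exposure e_i:

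- planned mean = (1/34) × Σ(y_i / e_i)
- pooled rate = Σy_i / Σe_i
- for a single event in a participant with exposure e, planned mean / pooled rate = average exposure / e

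**Case A: one event, in the only participant who stops early (day d); 33 complete.** Per 100 patient-years, planned mean = 100 × (365.25/d)/34 and pooled rate = 100 × 365.25/(33 × 46 + d).

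| d | Planned mean | Pooled rate | Ratio |
|---|---|---|---|
| 3 | 358 | 24 | 14.9 |
| 7 | 153 | 24 | 6.4 |
| 14 | 77 | 24 | 3.2 |
| 21 | 51 | 24 | 2.2 |
| 28 | 38 | 24 | 1.6 |
| 35 | 31 | 24 | 1.3 |
| 46 (all complete) | 23 | 23 | 1.0 |

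**Case B: one event, in a completer; four others stop event-free at day d.** Planned mean = 100 × (365.25/46)/34 = 23.4. Pooled rate = 100 × 365.25/(30 × 46 + 4d).

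| d | Pooled rate | Ratio |
|---|---|---|
| 7 | 25.9 | 0.90 |
| 14 | 25.4 | 0.92 |
| 21 | 24.9 | 0.94 |
| 35 | 24.0 | 0.97 |

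**Case C: stopping unrelated to events; four stop at day d.** With Poisson events at a common rate both estimators are unbiased. The ratio of their SDs is [√Σ(1/e_i) / 34] / √(1/Σe_i). At d = 7, Σ(1/e_i) = 30/46 + 4/7 = 1.224 and Σe_i = 1408, so the ratio is (1.106/34) / 0.02665 = 1.22. For d = 3, 14, 21 and 35 it is 1.55, 1.08, 1.03 and 1.00.

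**Precision of the pooled rate, all complete.** Exposure = 34 × 46 / 365.25 = 4.28 patient-years. The exact Poisson 95% limits on the count are 0 to 3.689 for no events and 0.0253 to 5.572 for one. Dividing by 4.28 and multiplying by 100:

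- no events: 0 (0 to 86) per 100 patient-years
- one event: 23 (0.6 to 130) per 100 patient-years

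**The case against.** The best defence is that the method is disclosed: the cell says the rate is formed for each patient, so the plan does not contradict itself. The row is descriptive, in a single-arm exploratory study, with no test or decision rule attached.

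The large multiples also need an unlikely coincidence. If events are unrelated to stopping, the chance that a single event falls in the early stopper is that participant's share of exposure: 7/1525 = 0.5% at day 7 and 14/1532 = 0.9% at day 14. With four stoppers the shares are 28/1408 = 2.0% and 56/1436 = 3.9%. Protocol 7.1 expects discontinuation to be uncommon. Protocol 7.2 does not name severe hypoglycemia as a reason for withdrawal, and Protocol 4.3.2 allows insulin to be reduced for safety without stopping treatment. Every severe episode is a serious adverse event with a narrative (SAP 6.10.6), and total patient-years are reported, so a reader could work out the pooled rate.

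Much of this stands. It means the 14.9 and 6.4 multiples are extremes rather than expected errors, and it keeps the point modest. It does not make the row adequate. The coincidence is improbable only if severe events do not cause stopping, which the documents do not establish. Rebuilding the rate takes care: the listing of severe events runs from Visit 3 through Visit 801 and the registry counts in SAP 6.14 include serious events that are not treatment-emergent, whereas the rate covers first to last dose. No planned output joins the count to the exposure. That other adverse event summaries also lack intervals does not help a reader faced with a zero rate on so little exposure.

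**Conclusion.** The concern holds. The plan specifies only a summary of per-patient ratios, with no pooled rate and no interval for severe hypoglycemia.

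The size of the discrepancy depends on where an event falls. It is nil if all complete, up to about 10% low in Case B, and several-fold high only when an event occurs in someone who stops within about the first two weeks. Those figures rest on the assumed stop days, one event and 46 days of exposure for completers. Without event-driven stopping, the cost is extra variability rather than bias.

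The zero-event case is the more practical gap: the row would show 0 with no sign that the upper limit is 86 per 100 patient-years. The change is worth making because it is simple, but no primary or secondary endpoint depends on it.

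**What to change.** In SAP Table ITSZ.6.4, define the rate as total severe hypoglycemia events divided by total patient-years of exposure in the Treated Population, times 100, over the first-to-last-dose window already set for this summary, with an exact Poisson 95% confidence interval. Show the event count and the patient-years with it.

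Keep the incidence row alongside, because the Poisson interval is too narrow if one participant has repeated events. The per-patient summary may stay as supplementary output, provided it is not labelled as the study event rate.

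The cost is one line in the SAP and one output row. The denominator is already planned in SAP 6.10.1, and no new data are needed.

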6.10.3.2. Injection Site Reaction

The injection site reactions will be searched by MedDRA PTs from all TEAEs. The number and percentage of patients experiencing treatment-emergent injection site reaction will be summarized.

6.10.4. Clinical Laboratory Evaluation

The data from safety laboratory measures will be only collected at Visit 1 for patient eligibility and safety. Therefore, no summary will be provided.

6.10.5. Vital Signs and Other Physical Findings

Post-baseline measurements and change from baseline to post-baseline for vital signs (systolic blood pressure [SBP], diastolic blood pressure [DBP], pulse rate) and physical characteristics (weight, BMI) at the scheduled visits will be summarized for patients who have both baseline and at least 1 post-baseline result.

The measurements during the treatment period will be analyzed by MMRM model similar to that for the primary endpoint, i.e., with baseline value of the response variable, visit as fixed factors and patient as the random factor.

6.10.6. Patient Narratives

Patient narratives will be provided for all patients in the study who experience any of the following “notable” events prior to data cutoff for the submission, if any occur during the study:

- deaths
- SAEs
- discontinuations from study (or study drug) due to AEs
- pregnancy

A list of patients who meet the criteria for narratives will be provided.

6.11. Important Protocol Deviations

Important protocol deviations, as defined in the Trial Issue Management Plan (TIMP), will be summarized for the Treated Population. The listing of important protocol deviations for the Treated Population during the entire study, will be provided in the CSR. No per-protocol population is planned for any analyses.

6.12. Interim Analyses and Data Monitoring

No interim analyses are planned for this study. If an unplanned interim analysis is deemed necessary, the appropriate Lilly medical director, or designee, will be consulted to determine whether it is necessary to amend the protocol.

6.13. CGM Analyses

The analyses described in Section 6.13 will include data collected from first dose of Humalog used during the lead-in period to the last IP used during the treatment period, excluding data (if any) that are collected while patients are temporarily off Humalog or IP.

All CGM outcome variables will only be derived for Visit 3 (baseline) and Visit 14 (endpoint) based upon the CGM data collected from valid CGM days, excluding data (if any) that are collected while patients are temporarily off Humalog during the lead-in period or temporarily off IP during the maintenance period. A valid CGM day to be counted into the calculation for a visit must have at least 70% of the total measures that are supposed to be obtained.

[Table ITSZ.6.5](#) lists all numerical measures for CGM data.

To ensure that the CGM outcome variables are only calculated from CGM session days with sufficient data within the 24-hour, daytime (0600 hours to midnight), or nighttime (midnight to 0600 hours) periods, the following criteria will be used to determine a valid CGM session day to be counted into the calculation for a visit: minimum number of measures per day – at least 70% of the total measures that are supposed to be obtained, i.e., 70% of the 288 measures for the 24-hour period;

Similarly, for the by-meal outcome variables, the following criteria will be used to determine a valid CGM session day for a visit: minimum number of measures per day – at least 70% of the

total measures that are supposed to be obtained. For example, 70% of the 24 measures for the $iAUC_{0-2hr}$ after breakfast.

The definition and derivation of these variables are described in detail in [Appendix 1](#).

Table ITSZ.6.5. Outcome Measures of CGM Data

Category	Endpoints	24-Hour	Daytime ^a	Nighttime ^b	By Meal ^c
Efficacy Endpoint: Glucose in the Target Ranges					
	Duration (in minutes) and percentage of time with sensor glucose values within target range 70 to 180 mg/dL [3.9 and 10.0 mmol/L], both inclusive (Primary Efficacy Endpoint)	X	X	X	
Efficacy Endpoint: Incremental AUCs (iAUCs) (after the start of meals)					
	$iAUC_{0-1hr}$				X
	$iAUC_{0-2hr}$				X
	$iAUC_{0-3hr}$				X
	$iAUC_{0-4hr}$				X
Efficacy Endpoint: Mean Glucose Excursions (after the start of meals) ^d					
	mean sensor glucose excursions 0 to 1 hour				X
	mean sensor glucose excursions 0 to 2 hour				X
	mean sensor glucose excursions 0 to 3 hour				X
	mean sensor glucose excursions 0 to 4 hour				X
Efficacy Endpoint: Hyperglycemia					
	Duration (in minutes) and percentage of time with glucose values >180, 181-250 and >250 mg/dL [10.0, 10.1-13.9 and 13.9 mmol/L]	X	X	X	
Efficacy Endpoint: Daily CGM Data Summary					
	Mean sensor glucose	X	X	X	
	Median sensor glucose	X	X	X	
Efficacy Endpoint: Glucose Variability and Risk Assessment					
Within-Day	CV	X	X	X	
	SD	X	X	X	
	IQR	X	X	X	
Between-Day	CV	X	X	X	
	SD	X	X	X	
Overall ^e	CV	X	X	X	
	SD	X	X	X	
	IQR	X	X	X	

Efficacy Endpoint: Highest Postprandial Glucose					
	Time from start of meal to the highest postprandial glucose level (minutes) within 4 hours after meal(s)				X
	Highest postprandial glucose level within 4 hours after meal(s)				X
	Highest postprandial glucose excursion level within 4 hours after meal(s)				X
Safety Endpoint: Hypoglycemia ^f					
	Duration (in minutes) and percentage of time with sensor glucose values <54, 54-69 and <70 mg/dL [3.0, 3.0-3.8 and 3.9 mmol/L]	X	X	X	X

Abbreviations: AUC = area under curve; CGM = continuous glucose monitoring; CV = coefficient of variation; hr = hour; IQR = interquartile range; SD = Standard deviation.

- ^a Daytime: 0600 hours to midnight (06:00:00-23:59:59 on the 24-hour clock).
- ^b Nighttime: midnight to 0600 hours (00:00:00-05:59:59 on the 24-hour clock).
- ^c By meals: for morning (breakfast), midday (lunch) and evening (dinner) meals and overall (average across all meals). The start time of morning, midday and evening meals are determined as the first entry in the CGM data during [04:00:00, 11:00:00], (11:00:00, 15:00:00] and [17:00:00, 21:00:00], respectively. When calculating time in ranges (target, hypo, hyper) for meals (0 to 1 hour, 0 to 2 hours, 0 to 3 hours and 0 to 4 hours), any data that are collected after the next meal event will be excluded.
- ^d Mean sensor glucose measured at different time points (1, 2, 3 or 4 hours) after the start of the meal minus mean sensor glucose at the start of meal
- ^e Overall variability refers to the variability calculated based upon all the CGM measurements collected across all valid days for each derivation period
- ^f In addition, postprandial hypoglycemia during the following time interval after each meal and overall will also be derived: 0 to 1 hour, 0 to 2 hours, 2 to 4 hours, 0 to 4 hours. The calculation will exclude the data from patients who have had the next meal event before the end of time interval.

The proportion of patients who have achieved the guidance (Battelino 2019) recommended CGM targets of glycemic control (Table ITSZ.6.6) during the lead in period (baseline) and the maintenance period (endpoint) will be summarized.

Table ITSZ.6.6. Guidance Recommended CGM Targets of Glycemic Control

Percentage of time with sensor glucose (24-hour)	Guidance Recommendation
target range	
70-180 mg/d.L (3.9-10.0 mmol/L, both inclusive)	>70%
hypoglycemia range	
<54 mg/dL (3.0 mmol/L)	<1%
hyperglycemia range	
>250 mg/dL (13.9 mmol/L)	<5%

Other than that, all continuous variables (actual and change from baseline, if applicable) will be analyzed by using the ANCOVA defined in Section 6.1.

In addition, the following standardized glucose summary reports from the ambulatory glucose profile (AGP) will be generated, based upon all the observed CGM data during the lead in period and the maintenance period, regardless of whether they are collected on valid CGM days:

- 24-hour period at individual patient level
- 24-hour period at the treatment level
- 0 to 4 hours relative to meal starting time, excluding data collected after the next meal event (if any is captured within the interval) at the treatment level
- 0 to 4 hours relative to meal starting time, by meal (breakfast, lunch, and dinner) and by infusion set wear day excluding data collected after the next meal event

